## Study Procedures

**If you uploaded a separate research protocol document in the 'Research Protocol' page, cite the applicable section and page numbers from that document in the answer boxes below. (If this study is a collaborative UM/VA study please list each procedure that is being conducted and the locations where it is being conducted.)**

1 \* Describe all procedures being performed for research purposes only (these procedures would not be done if individuals were not in the study) and when they are performed, including procedures being performed to monitor subjects for safety or to minimize risks:

Patients will be identified at random in the orthopaedic trauma clinic and current admitted patients who have been diagnosed with an infection. Once eligibility has been confirmed, the informed consent process will be completed by the Research Coordinator and the attending surgeon. Patients will be approached about potential participation in the study as soon as is feasible following determination of eligibility.

Once consented into the study, baseline data regarding participant characteristics, injury characteristics, fracture classification and medical history/co-morbidities will be collected. Characteristics about hospital course and treatment received will also be collected (i.e. blood culture results, antibiotic usage, etc).

At each follow up visit, participants will undergo a clinical evaluation by the treating surgeon as part of standard of care following any surgical procedure and will be interviewed by the research coordinator. Blood draws will be taken at the initial and each subsequent visit and will be analyzed in the laboratory of one of the investigators in the study. If the patient is currently infected currently, or become infected at any point in the future, additional blood draws may be taken, at a maximum of 10 draws, over the period of two years from the clinical diagnosis of infection. The amount of blood that is drawn will not exceed 50 ml or 3 ml per kg in a 8 week period, and collection may not occur more frequently than 2 times per week.

Finally, we would prospectively correlate the laboratory findings with clinical findings by searching the patients' medical records to find outcomes such as a biofilm formation.

2 \* Describe all procedures already being performed for diagnostic or treatment purposes (if not applicable to the study, enter "N/A"):

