As part of the routine standard of care for any patient readmitted to the hospital for suspected surgical site infection cultures are obtained and sent for laboratory analysis to confirm bacterial colonization. As this is an assay to identify earlier a surgical site infection, this would be done earlier than any current testing.

3 \* Describe the duration of an individual participant's participation in the study:

Following index clinic blood draws, patients will be followed during their regularly scheduled visits with their surgeon to assess wound healing.

4 \* Describe the amount of time it will take to complete the entire study:

The study will last 1-2 years in total.

5 \* Describe any additional participant requirements:

There are no additional requirements.

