## Research Related Risks

If you uploaded a separate research protocol document in the 'Research Protocol' page, cite the applicable section and page numbers from that document in the answer box below.

1 \* Individually list each research-related risk, using a separate line for each. Next to each risk, delineate the likelihood/seriousness of the risk, and the provisions for minimizing the risk:

1. Blood draw - risk of further bleeding and site infection. Minimal risk. Unlikely that the patient will experience complications as it will be drawn in concordance with other laboratory requirements by either a nurse or lab technician. If no other laboratory requirements on the day of the visit, will still draw one vial per visit. Safety issues related to this are only concerns related to patient privacy.

ID: VIEW4E1B52509F000  
Name: v2\_Research Related Risks

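### Research draws precede culture by schedule, and the stated analysis makes no comparison that would separate early detection from chance positives

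*Combined protocol and SAP*

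**What the plan says.** **Timing of the assay.** Study Procedures, item 1: "Blood draws will be taken at the initial and each subsequent visit and will be analyzed in the laboratory of one of the investigators". Research Related Risks confirms that the draw needs no clinical trigger: "If no other laboratory requirements on the day of the visit, will still draw one vial per visit".

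**Timing of current testing.** Study Procedures, item 2, describes standard care: "for any patient readmitted to the hospital for suspected surgical site infection cultures are obtained and sent for laboratory analysis". The next sentence reads: "As this is an assay to identify earlier a surgical site infection, this would be done earlier than any current testing".

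**Clinical evaluation.** Study Procedures, item 1: "At each follow up visit, participants will undergo a clinical evaluation by the treating surgeon as part of standard of care". The surgeon's evaluation and the research draw therefore fall on the same visits.

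**Who is sampled.** Justification, Objective, & Research Design, item 2, allows patients to be infected or not infected when blood is drawn. The first inclusion criterion admits patients with a known infection. Study Procedures and Prospective Samples also provide for draws after diagnosis.

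**Analysis.** Sample Size and Data Analysis, item 2, offers descriptive statistics, t-tests and other methods as suitable. Study Procedures, item 1, adds a correlation of laboratory with clinical findings from the record. No positivity cut-off, detection window, definition of lead time, accuracy measure or primary comparison is given.

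**The concern.** Early detection is the purpose of the study: it is in the title, in the stated aim and in the benefit described in the Lay Summary. For a patient enrolled before infection, the visit calendar sets the time of the assay and clinical suspicion sets the time of culture. A positive assay at an earlier visit then precedes culture whether or not the assay carries any information. The order of the two dates says nothing about performance.

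What would say something is whether pre-diagnosis draws are positive more often in patients who later become infected than in comparable patients who do not. The stated analysis does not ask this. A t-test or correlation that pools all draws would mix pre-diagnosis samples with samples from patients already known to be infected. It could show an association driven entirely by established infection. At stake is whether data from 1000 to 1200 patients can answer the early-detection question, or will yield an apparent lead time that cannot be told from sampling order.

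**Working it through.** The plan gives no figure for lead time, sensitivity or false positives, so there is nothing to reproduce. The check asks how often an assay with no information would be positive before culture.

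**Inputs**
- k, the number of research draws before diagnosis: 1 to 3, from the range in the Research Design section. That range is for all draws, so assuming that every one precedes diagnosis is a simplification. Study Procedures implies a draw at every visit, which could give more; k = 5 is shown for that case.
- f, the chance that a single draw is positive regardless of infection: not in the documents; assumed 5%, 10% and 20%.
- Draws are assumed independent. Positive correlation within a patient would pull the results for k above 1 down towards f.

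**Step 1. Share of later infections with at least one chance positive before culture: 1 − (1 − f)^k**

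| f | k = 1 | k = 3 | k = 5 |
|---|---|---|---|
| 5% | 5.0% | 1 − 0.95³ = 14.3% | 22.6% |
| 10% | 10.0% | 1 − 0.90³ = 27.1% | 41.0% |
| 20% | 20.0% | 1 − 0.80³ = 48.8% | 67.2% |

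Over 1 to 3 draws the range is about 5% to 49%.

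**Step 2. What that means in patients.** Take 1000 patients, an assumed 10% infected after enrolment, k = 3 and f = 5%. Of 100 infected patients, 100 × 0.143 ≈ 14 would look detected early. Of 900 uninfected patients, 900 × 0.143 ≈ 128 would also be positive at least once. Reported alone, the 14 look like a finding; beside the 128 they do not.

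**Step 3. Does a comparison with uninfected patients expose it?** Assume visits at weeks 2, 6 and 12 and a culture date uniform over weeks 1 to 52, independent of the assay. Then 1/51 of infections have no prior draw, 4/51 have one, 6/51 have two and 40/51 have three. At f = 5% the share with a pre-culture positive is (4 × 0.05 + 6 × 0.0975 + 40 × 0.1426)/51 = 12.7%. The same sum gives 24.3% at f = 10% and 44.1% at f = 20%. Uninfected patients observed over the same window have the same expected share. A simulation of 100,000 pairs agrees:

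| f | Later infected | Uninfected, same window | Uninfected, all three visits |
|---|---|---|---|
| 5% | 12.7% | 12.7% | 14.3% |
| 10% | 23.9% | 24.5% | 27.3% |
| 20% | 44.1% | 43.9% | 48.8% |

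In the same simulation every pre-culture positive had a lead above zero. The median lead was about 23 weeks, and about 91% of the leads were 4 weeks or longer, all from an assay with no information. These lead times depend on the assumed visit and culture dates.

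The window-matched comparison shows no difference, which is correct for a useless assay. The last column shows why matching is needed: uninfected patients contribute more draws, so an unmatched comparison would be biased against the assay.

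**The case against.** The strongest reply is that no faulty analysis is actually planned. The sentence about earlier testing answers a form question on standard-of-care procedures. It describes when the test is done and is not offered as a result. No rule anywhere makes a chance positive count as a detection. A reader might infer that the plan specifies a biased lead-time analysis; the documents do not support that. The problem is an unguarded risk.

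A reader might also infer that the design cannot tell true lead time from an artefact. That too goes further than the text. Non-infected patients are sampled, draws occur at the same visits as the clinical evaluation, and Sharing of Results keeps assay results from treating surgeons. The third step above shows that such data would expose a useless assay. The gap lies in the written analysis.

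Three further limits stand. Patients infected at entry and draws after diagnosis are not affected. The artefact is against culture; the only lead time the plan cites, from an animal model in the Lay Summary, is against clinical detection, and the surgeon examines patients at the same visits. The follow-up and infection-diagnosis forms listed under Additional Documents are not available, so they may already record same-day status.

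None of this supplies the missing comparison. Followed as written, t-tests and an unspecified correlation do not isolate the draws that bear on early detection.

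**Conclusion.** The point holds for patients enrolled before infection. Any positive before culture is earlier by schedule and is not evidence of performance, and the stated analysis has no safeguard against counting chance positives as early detection.

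For an uninformative assay, about 5% to 49% of later infections would carry at least one such positive. This rests on an assumed per-draw positive rate of 5% to 20%, on 1 to 3 independent draws, and on all of them preceding diagnosis. With more draws the share rises; with correlated draws or fewer pre-diagnosis draws it falls. It is tempting to conclude that any useless assay would appear to detect infection early. The arithmetic supports this only for a fraction of infections: the share is 0% for an assay that is never positive and 100% only for one that is always positive.

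The number of draws drives the size, and the documents disagree on it. The Research Design section gives 1 to 3, Study Procedures gives every visit with up to 10 in infected patients after diagnosis, and Prospective Samples also gives up to three during hospitalization for diagnosed infection. These statements must be reconciled.

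**What to change.** Before assay results are linked to outcomes, write the early-detection analysis into Sample Size and Data Analysis:

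1. Fix the positivity cut-off.
2. Use only draws taken on dates when the same-day clinical evaluation recorded no infection. Exclude patients infected at entry and all post-diagnosis draws; these can be analysed separately.
3. Compare positivity in later-infected and never-infected patients at matched visits, or over the same observation window, with equal numbers of draws. Report sensitivity and specificity, or the AUC, with confidence intervals.
4. Where the record holds same-day clinical findings and routine blood results, report them as paired comparators on the same draws. The recorded diagnosis is negative on all these draws by selection, so the clinical comparator has to be the finer findings noted that day.
5. Do not treat the fact that the assay is done earlier as evidence of early detection unless this comparison supports it.
6. Reconcile the statements on the number of draws.

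The cost is some extra chart abstraction, within a record search already planned, and some analysis time. Fewer draws will be usable, and the early-detection claim becomes harder to meet. No added draws or patients are needed.

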## Sample Size and Data Analysis

**If you uploaded a separate research protocol document in the 'Research Protocol' page, cite the applicable section and page numbers from that document in the answer boxes below.**

1 \* Provide the rationale and sample size calculations for the proposed target population:

In order to validate the designed test, we hypothesize needing a large study to determine if it is effective in a human model. Additionally, we will follow out the patients to determine if some become infected (the primary outcome of the study that we are trying to ultimately be able to predict. We anticipate 1000-1200 patients enrolled in this study).

2 \* Provide the plan for data analysis. Include in the description the types of comparisons that are planned (e.g., comparison of means, comparison of proportions, regressions, analysis of variance, etc.), which is the primary comparison/analysis, and how the analyses proposed will relate to the primary purposes of the study:

We will describe the population in terms of general descriptive statistics for age, injury, surgery and outcome. We will use t-testing and other statistical analysis as appropriate.

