## Lay Summary

1 \* Provide a summary of the background and purpose of the study in language that can be understood by a person without a medical degree.

Surgical site infection in the orthopaedic surgery population is a significant public health issue. Wound infections result in both increased length of hospital stay and total cost of care.

Surgical site infection (SSI) is the most common preventable adverse outcome after a major operation. The economic costs to the US healthcare system are enormous estimated to be in excess of \$1.8 billion per year. For patients who develop an SSI, the cost may be even higher with length of stay and risk of death doubled. Thus the benefits of any intervention decreasing the risk of SSI are very tangible.

A biofilm is a layer of bacteria that adheres to a surface; in Orthopaedics, this often means adherence to implanted metal after fracture surgery. The test that has been designed by one of the investigators on the study has been shown in an animal model to detect the formation of a biofilm up to 1 month prior to clinical detection. Having a blood assay such as this would allow earlier antibiotics and potentially prevent the need for further surgeries to remove metal implants and clean out the biofilm.

ID: VIEW4E02805CF7000  
Name: v2\_Lay Summary

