## Justification, Objective, & Research Design

**If you uploaded a separate research protocol document in the 'Research Protocol' page, cite the applicable section and page numbers from that document in the answer boxes below.**

1 \* Describe the purpose, specific aims, or objectives of this research. State the hypothesis to be tested:

To determine if a new assay to detect early biofilm colonization can be validated in acute postoperative wound infections in orthopaedic trauma patients who have sustained high energy open/closed lower extremity fractures. This would potentially help decrease the amount of surgical interventions needed for infections as it could allow for early intervention and antibiotics.

2 \* Discuss the research design including but not limited to such issues as: probability of group assignment, potential for subject to be randomized to placebo group, use of control subjects, etc.:

A prospective trial conducted at Shock Trauma of patients between 18 years of age and older who have sustained a fracture with metal implanted. We will be collecting between 1-3 routine blood draws for the purpose of laboratory analysis to assess biofilm growth. Patients may be infected or non-infected at the time of blood draw; they will be selected at random for purposes of this study. All patients will be followed as standard of care by their treating physician for all their follow up visits.

3 \* Describe the relevant prior experience and gaps in current knowledge. Describe any relevant preliminary data:

Surgical site infection in the orthopaedic surgery population is a significant public health issue. Wound infections result in both increased length of hospital stay and total cost of care. Specifically, a biofilm assay would help identify early infection in patients and potentially reduce the need for re-operations for infections as it would allow early antibiotic delivery to the affected areas. Our bacteria of focus would be Methicillin-resistant Staphylococcus aureus (MRSA), as this is one of the most predominant organisms in orthopaedic surgical site infections, but can be included to other pathogens causing surgical site infections.

4 \* Provide the scientific or scholarly background, rationale, and significance of the research and how it will add to existing knowledge:

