**Number Criteria**

View 1	Previous fracture fixation with an implant (intramedullary nail, plate, screws), or joint revisions, or periprosthetic fracture, or admitted from orthopaedic trauma clinic due to infection, or inpatient with a known infection.
View 2	Age 18 and older
View 3	English speaking

List exclusion criteria (List each Exclusion Criteria individually, using the ADD button):

Number	Criteria
View 1	Patients with planned follow-up at another medical center
View 2	Patient lives outside of the hospital catchment area

After entering the inclusion and exclusion criteria above, click the Save link. CICERO will automatically generate a printable Eligibility Checklist for you to use in your research. To review the checklist, click on the resulting link below. This checklist is also available under the Documents tab of this application.

Eligibility Checklist for HP-00055743\_7 v10-6-2015-1444148031816(0.01)

ID: VIEW4E0E5185F9000  
Name: v2\_Eligibility

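### Becoming infected is the primary outcome to be predicted, but it has no time horizon, minimum follow-up or defined index draw, and the only named test, the t-test, cannot allow for unequal follow-up

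*Combined protocol and SAP*

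**What the plan says.** - **Outcome.** Sample Size and Data Analysis, item 1: "we will follow out the patients to determine if some become infected (the primary outcome of the study". No window is attached.
- **Analysis.** Item 2 of that section offers descriptive statistics and then "We will use t-testing and other statistical analysis as appropriate". It gives no censoring, time-to-event or fixed-window rule.
- **Individual follow-up.** Study Procedures, item 3, asks how long each participant takes part. The answer is that "patients will be followed during their regularly scheduled visits with their surgeon to assess wound healing", after index draws taken in clinic. It gives no length, minimum or end date, and the index draws are not defined.
- **Study length.** Study Procedures, item 4: "The study will last 1-2 years in total". Enrolment and follow-up are not separated.
- **Draws.** Study Procedures, item 1: "Blood draws will be taken at the initial and each subsequent visit". No draw is singled out as the one to be tested against later infection.
- **Who enters.** Justification, Objective, & Research Design, item 2: "Patients may be infected or non-infected at the time of blood draw". Inclusion criterion 1 also admits patients "or admitted from orthopaedic trauma clinic due to infection, or inpatient with a known infection".
- **Lead time.** The Lay Summary says the assay was shown in an animal model "to detect the formation of a biofilm up to 1 month prior to clinical detection".
- **The only stated window.** Study Procedures and Prospective Samples allow extra draws for two years after infection is diagnosed. This limits sampling and does not set an outcome horizon.

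**The concern.** A prediction target needs a starting point and a window. Without them, whether a patient counts as uninfected can depend on enrolment date. Someone enrolled in the first month and someone enrolled in the last could both enter the comparison as uninfected, one after a year or more of observation and the other after a few weeks. Because blood is drawn at every visit, the time observed after a draw also differs between draws on the same patient.

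A t-test needs two groups fixed in advance and takes no account of how long each patient was watched. Patients who go on to be infected after the close would sit in the comparison group and blur the contrast meant to validate the assay, and their events would be lost as cases. If the window is chosen after the data are in, the result can also depend on that choice.

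This concerns only patients infection-free at the draw. Those already infected at entry have a known status and need no horizon.

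**Working it through.** **1. The plan's own figure.** The target of 1,000-1,200 patients comes with no error rate, power, effect size, infection rate or target accuracy. It cannot be reproduced, and it does not show what observation time was intended.

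**2. Inputs for an illustration.** From the documents: study length T = 12 or 24 months. Assumed, because the documents are silent:
- even accrual up to the day of close, so follow-up u is uniform on (0, T);
- exponential time to infection from the enrolment draw, median 3 or 6 months, with distribution function F(t) = 1 − exp(−λt) and λ = ln 2 / median;
- horizons h of 1, 3, 6 and 12 months.

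**3. Formulas.**
- Patients enrolled less than h before close: h/T.
- Within-horizon infections unseen at close: 1 − mean over u of F(min(u, h))/F(h). Under even accrual this reduces to (1/T) × [1/λ + h − h/F(h)].

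Worked case, T = 12, h = 6, median 3: 1/λ = 4.328 and F(6) = 0.75, so (4.328 + 6 − 8)/12 = 0.194. With median 6: 1/λ = 8.656 and F(6) = 0.5, so (8.656 + 6 − 12)/12 = 0.221.

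**4. Results, accrual to close.**

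| Horizon | Short follow-up, T = 12 / 24 | Infections unseen, T = 12 (median 3, 6) | Infections unseen, T = 24 (median 3, 6) |
|---|---|---|---|
| 1 month | 8% / 4% | 4.0%, 4.1% | 2.0%, 2.0% |
| 3 months | 25% / 12.5% | 11.1%, 11.8% | 5.5%, 5.9% |
| 6 months | 50% / 25% | 19.4%, 22.1% | 9.7%, 11.1% |
| 12 months | 100% / 50% | 29.4%, 38.8% | 14.7%, 19.4% |

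**5. Sensitivity to the assumptions.**
- *Enrolment closes halfway* (u uniform on T/2 to T): the loss is 0% in every cell except T = 12, h = 12, where it is 7.8% (median 3) or 14.8% (median 6).
- *Infections spread evenly over the horizon*: the unseen share is h/(2T). The largest value is 12/24 = 50% (T = 12, h = 12).
- *Longer study*: under accrual to close, the unseen share falls in proportion to 1/T for any horizon within the study length.

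**6. What this does not give.** These are shares of infections, not of patients. How far the uninfected group is contaminated also depends on the infection rate, which is not stated. No case count, sensitivity or specificity figure follows.

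**7. Duration against the sampling window.** A patient diagnosed at any time after study start cannot complete a two-year post-diagnosis window inside a study of at most two years. The two statements need reconciling.

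**The case against.** - **An index draw is mentioned.** A reader might infer that the plan has none at all. That is too strong, because Study Procedures, item 3, starts follow-up from index draws in clinic. The phrase is undefined, does not fit inpatients who enter with a known infection, and links no draw to the outcome. The gap is one of definition.
- **No grouping rule is written.** A reader might infer that the plan instructs analysts to count briefly followed patients as uninfected. It does not, and its reference to other suitable analysis leaves room for censored-data methods. What stands is that nothing prevents such grouping, and the one method named cannot handle unequal follow-up.
- **Prediction is only part of the aim.** The objective is framed as validating the assay in acute postoperative infection, and infected patients are enrolled too. The share of the sample affected is unknown. Even so, the plan calls later infection the primary outcome.
- **The size rests on assumptions.** At the only lead time in the documents, the loss is 2-4%, and that is under accrual that is near worst case. No section suggests a 12-month horizon. Draft consent forms listed with dates from 2015 to 2018 hint at a project longer than two years, which would shrink every figure, although they do not establish accrual dates. All of this stands.
- **Ascertainment is better than the visit schedule suggests.** Record search, phone contact with patients who do not return, and exclusion of patients followed elsewhere all help to find infections. They do not set a common observation time.
- **Unseen forms.** The Follow-Up and Diagnosis of Infection forms are listed but not available, so a rule there cannot be excluded. The window for the primary outcome belongs in the analysis plan in any case.

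**Conclusion.** The point holds and should be fixed. As written, the primary outcome has no horizon or minimum follow-up and no defined draw from which to count, and it is paired with a test that ignores observation time. Among patients infection-free at the draw, late enrolment can therefore pass for absence of infection.

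The documents do not fix the size. In the illustration with exponential timing it runs from 0%, when enrolment closes early enough, to 29-39% of within-horizon infections unseen for a 12-month horizon in a 1-year study. A reader might infer that a large bias has been shown. It has not: the result turns on accrual pattern, horizon and infection timing, none of which the plan states.

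Two further inferences are not supported. The mismatch between study length and the two-year sampling window is not a breach, because that window is an optional ceiling; it is wording to reconcile. The statements that identifiers will be destroyed after initial data analysis (Prospective Data; Waiver/Alteration of Authorization) are not a plan to destroy them before outcomes are linked. They leave the order open, which is a separate, minor clarification.

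**What to change.** **Sample Size and Data Analysis**
- For patients infection-free at a named index draw (the enrolment draw, for example), define the outcome as infection within one prespecified horizon after that draw. Justify the horizon against the lead time in the Lay Summary.
- Replace the simple t-test for this outcome with a censored-data method (time-to-event, or time-dependent accuracy), censoring uninfected patients whose follow-up is shorter than the horizon.
- Report the number observed to the horizon.
- Analyse patients already infected at entry separately.

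**Study Procedures**
- State duration as enrolment period plus follow-up, and reconcile it with the two-year post-diagnosis sampling window given there and in Prospective Samples.

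**Cost.** This is mostly wording and a standard analysis, with no new visits or draws. Checking every patient at one horizon adds some record search and calls, and phone contact is at present described only for patients who will not return.

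If every patient must reach the horizon, either the stated duration lengthens or enrolment closes earlier. For a 6-month horizon:
- 2-year study: 18 months to enrol, so 1,000/18 to 1,200/18 = 56-67 patients a month, against 42-50 over 24 months.
- 1-year study: 6 months to enrol, so 1,000/6 to 1,200/6 = 167-200 a month, against 83-100 over 12 months.

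A 12-month horizon would leave a 1-year study no enrolment period. If the stated duration is kept, censoring limits this cost, because patients with shorter follow-up still contribute the time they were observed.
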